7.8 Early Withdrawal/Premature Discontinuation of Subjects

Subjects may be withdrawn early from the study for a number of reasons, including:

- Subjects experiencing a failed LITT treatment attempt. A failed LITT treatment attempt is defined as stopping the procedure prior to thermal delivery. (Subjects that experience a failed treatment attempt will be followed for 1 month post-procedure for related adverse events.)
- Subject death
- Subject lost to follow-up
- Subject request for withdrawal
- Adverse events
- Investigator decision (other than an adverse event)

If a study subject is discontinued from the study early, a Study Completion CRF must be completed describing the reason for early discontinuation. The investigator should make all attempts to conduct an Early Withdrawal visit at the time of withdrawal from the study. If a subject has withdrawn consent for the study or is lost to follow-up, the completion of this visit is not imperative. In situations where study withdrawal is due to an adverse event, subjects will be followed until resolution of the adverse event or determination that the subject's condition is stable.

At the Early Withdrawal visit, the subject will undergo the following evaluations:

- QOLIE-31. It is preferred that the subject completes the questionnaire prior to any other tests.
- Neurological exam (cranial nerves (including confrontation visual field testing), motor, coordination, reflexes, gait, sensation)
- Neuropsychological testing
- Adverse event monitoring
- Subject satisfaction
- Functional assessment (including employment status, education, living arrangements, driving status)
- Surgical outcome classifications (Engel and ILAE, see Appendix D)

If a subject chooses to withdraw from the study and also withdraws consent for disclosure of future information, no further evaluation(s) should be performed and no additional data will be collected. The Sponsor may retain and continue to use any data collected prior to the withdrawal of consent.

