Surgical outcome classification will be reported by tabulating the Engel and ILAE class frequency distribution at each scheduled follow-up among subjects completing that follow-up visit. The change in surgical classification between visits may be described by performing a cross-tabulation of the classifications at subsequent visits.

Freedom from seizures with altered awareness will be reported using Kaplan-Meier curve analysis of the time to first seizure, as reported in patient diaries. The time to event analysis will exclude seizures that occur within the first 4 weeks post-procedure. The Kaplan-Meier analysis may be repeated for freedom from all seizures, seizures with other classifications, and inclusion of seizures within the first 4 weeks post-procedure. The log-log transformation will be used to calculate 95% confidence intervals. The time point of primary interest is 24 months.

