10.2.2 Analysis Populations

All subjects enrolled in the study (including those withdrawn from the investigation) will be accounted for and documented.

The following analysis populations are defined:

Enrolled Set: All subjects enrolled in the study

Treated Set: All subjects that initiate treatment with LITT (received thermal delivery with the NBS)

Per-protocol Set: All subjects in the Treated Set that are treated according to the protocol requirements and meet study and treatment eligibility criteria

In the feasibility study setting, conclusions about performance are best informed by analyses of the Treated Set. Analyses may be repeated on the Enrolled Set for full reporting of study results and on the Per-protocol Set to provide insight into the potential impact of protocol deviations on the analysis results.

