10.2.3 Handling of Missing Data

The number and proportion of subjects eligible for and compliant with each follow-up examination will be presented. Subjects who withdraw from the study will be tabulated with reasons for withdrawal. Sensitivity analyses, such as multiple imputation or worst case imputation, may be performed to assess the robustness of study conclusions to the potential impact of missing data.

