11.1.3 Secondary Endpoint: Analysis of Seizure Outcomes

Surgical outcome classification will be reported by tabulating the Engel and ILAE class frequency distribution at each scheduled follow-up, among subjects completing that follow-up visit. The change in surgical classification between visits may be described by performing a cross-tabulation of the classifications at subsequent visits. The classifications are described in more detail in Appendix B.

For the Engle classification, there are several classification terms that can be subjective in nature, so further definitions are provided to the sites, as follows:

- the term “disabling seizures” includes all focal seizures *except*
 - those without impairment of consciousness or responsiveness (simple partial seizures) involving subjective sensory or psychic phenomena only
- The term “worthwhile improvement” is defined as $\geq 50\%$ seizure reduction compared to baseline.

Seizure frequency will be characterized by calculating the rate of seizure occurrence within specific follow-up time periods (count of reported events/reported time frame). Follow-up time periods of interest include all follow-up and between-visit follow-up periods (e.g., procedure to Month 3) to characterize the longitudinal course of seizure frequency. For each time period, descriptive statistics of subject-specific rates characterize the distribution of observed seizure rates. The change from baseline in seizure rates may also be calculated by calculating the difference in rate between a follow-up period and the baseline rate of seizures occurring prior to treatment (count of reported events/reported time frame). Since subjects may have different baseline seizure rates, the relative change from baseline in the event rate (r)

$$\frac{(r_{\text{follow-up}} - r_{\text{baseline}})}{r_{\text{baseline}}}$$

will also be calculated to scale the degree of improvement relative to the baseline rate. These analyses may be repeated for subsets of seizures with specific classifications to characterize the frequency of different seizure types.

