15.3 CEC Adjudication

In all tabulations of adverse events, the categorizations of adverse events determined by the CEC (e.g. relatedness of adverse events to the device treatment or procedure) will be reported, if available, and categorizations provided by investigators will be reported otherwise. Adverse event listings will report both CEC and investigator categorizations.

16 Interim Analyses

Analyses will be reported on data from baseline through a major study time point once all subjects have completed that major study time point (e.g., 6 months, 12 months and 24 months). There is minimal opportunity for bias since all procedures will have been completed before any analysis is reported and all data will have been collected for a time point before analysis of that time point is reported.

The study's DSMB may request descriptive analyses of accumulating data at its discretion.

17 Missing Data Analyses

Every effort will be made to reduce the incidence of missing data. The study will be conducted with proper screening of study subjects, complete training of participating investigators, study coordinators and monitors. All subject data that are available on subjects who drop out during the study will be included.

The number and proportion of subjects eligible for and compliant with each follow-up examination will be presented. Subjects who withdraw from the study will be tabulated with reasons for withdrawal. Sensitivity analyses, such as multiple imputation or worst case imputation, may be performed to assess the robustness of study conclusions to the potential impact of missing data.

In worst case imputation, for binary endpoints the worse of the two possible outcomes will be imputed. The timing of the imputed event will be the last known event-free date for subjects that exit the study prematurely. For continuous endpoints assessed at a single time period (e.g. quality of life), the worst observed value among subjects with observed data at that time period will be imputed for subjects with missing data. For rates corresponding to a specific follow-up time interval, any partial observed data for a subject will be used. Data for the missing portion of the subject's follow-up time interval will be imputed using the worst observed value among all subjects with observed data during the corresponding missing portion of the follow-up time interval, in order to calculate an imputed rate for the overall follow-up time interval.

18 Sensitivity Analyses

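### Engel and ILAE classes are tabulated among visit completers only, with no stated place for the Early Withdrawal class, so the Class I share may be overstated if subjects with persistent seizures leave more often

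*Protocol*

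**What the plan says.** Protocol 10.1.3 tabulates the Engel and ILAE class distribution "at each scheduled follow-up among subjects completing that follow-up visit". SAP 11.1.3 has the same rule: "at each scheduled follow-up, among subjects completing that follow-up visit".

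Other provisions that bear on it:

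- **Population.** Protocol 10.2.2 states that "conclusions about performance are best informed by analyses of the Treated Set"; SAP section 10 agrees.
- **Early Withdrawal visit.** Protocol 7.8 and the Early Withdrawal column of Table 2 in both documents call for the Engel and ILAE classes at this visit. Protocol 7.8 adds: "If a subject has withdrawn consent for the study or is lost to follow-up, the completion of this visit is not imperative".
- **Dropout data.** SAP section 17 says "All subject data that are available on subjects who drop out during the study will be included", without saying in which tables.
- **Missing data.** Protocol 10.2.3: "Sensitivity analyses, such as multiple imputation or worst case imputation, may be performed to assess the robustness of study conclusions". SAP section 17 is equally permissive. Its worst-case rules cover binary endpoints, continuous endpoints and rates, but not an ordinal class.
- **Time point.** SAP 12.7 names 24 months as a time point of primary interest for the study.

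**The concern.** By Month 24 the completers' table describes only the subjects who stayed. A treated subject who left at Month 8, say, counts in the Month 3 and Month 6 tables and in none after that, whatever the seizure outcome. If persistent seizures make withdrawal more likely, the share in Engel I or ILAE 1 rises over time partly because failures leave the denominator.

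The documents make such withdrawal plausible without establishing it. Adverse events, death, subject request and investigator decision are all listed reasons in Protocol 7.8. Worsening of a pre-existing condition counts as an adverse event under Protocol 9.1, and Protocol 11.1 lists increased seizures and SUDEP among the risks. A withdrawal coded as an adverse event or a death can therefore be a seizure failure.

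No test or error rate is at stake, because the endpoint is secondary and descriptive. What is at stake is a planning figure: Protocol 10.2.4 says the results from 30 subjects are meant to support planning of a larger pivotal trial.

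**Working it through.** **The plan's own figure.** The only sample-size figure concerns adverse events: an event with 5% probability per subject has about an 80% chance of being seen at least once in 30 subjects. 1 − 0.95^30 = 0.785, which agrees. It confirms n = 30 as the base but says nothing about Engel or ILAE class.

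**Inputs.** N = 30 treated (Protocol 10.2.4, SAP section 9). The documents give neither a dropout rate nor an expected Class I rate, so two inputs are assumptions: w = 3, 6 or 9 withdrawn by Month 24, and about 60% of completers in Class I.

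**Formulas.** Let c = N − w completers, of whom s are in Class I.

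- Completers' share: s/c
- Lower bound, all withdrawn are failures: s/N
- Upper bound, all withdrawn are successes: (s + w)/N
- Excess over the lower bound: s/c − s/N = (s/c)(w/N)
- Shortfall from the upper bound: (s + w)/N − s/c = (1 − s/c)(w/N)

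**Results.**

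| w | Completers | All withdrawn fail | All withdrawn succeed | Excess over lower bound | Shortfall from upper bound |
|---|---|---|---|---|---|
| 3 | 16/27 = 59.3% | 16/30 = 53.3% | 19/30 = 63.3% | 5.9 points | 4.1 points |
| 6 | 14/24 = 58.3% | 14/30 = 46.7% | 20/30 = 66.7% | 11.7 points | 8.3 points |
| 9 | 13/21 = 61.9% | 13/30 = 43.3% | 22/30 = 73.3% | 18.6 points | 11.4 points |

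Taking completer success from about 50% to 70% widens the excess over the lower bound to between 5.2 points (14/27 × 3/30) and 21.4 points (15/21 × 9/30).

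**A middle case.** If withdrawn subjects are half as likely as completers to be in Class I, the excess is half the worst case: 3.0, 5.8 and 9.3 points for w = 3, 6 and 9. It is zero if w = 0 or if leavers do as well as completers.

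**Sampling error for scale.** With w = 6, the exact 95% interval is 36.6% to 77.9% for 14/24 and 28.3% to 65.7% for 14/30.

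**Where the Early Withdrawal class goes.** SAP 15.2 assigns data to the time point named on the CRF. Early Withdrawal has its own column in Table 2 and is not a scheduled follow-up month. Read together with the completers rule, nothing moves that class into the Month 18 or Month 24 table. SAP section 17's general statement points the other way but names no table. The two need to be reconciled.

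**The case against.** Three stronger readings are tempting, and the documents do not support them.

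*A reader might infer that the Early Withdrawal class is thrown away.* SAP section 17 says available dropout data will be included. What can be said is that the class has no stated place in the by-visit tables.

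*A reader might infer that seizure success is overstated.* That requires leavers to do worse than completers. Protocol 7.8 introduces its list with "Subjects may be withdrawn early from the study for a number of reasons, including", and the list does not name seizure recurrence or lack of efficacy. One listed reason, a failed attempt stopped before thermal delivery, falls outside the Treated Set altogether. Repeat LITT for persistent seizures has its own in-study procedures (Protocol 7.7), and SAP 18.1 handles other epilepsy procedures up to Month 24 by censoring later visits in a sensitivity analysis. Both presuppose continued follow-up, so seeking further treatment need not mean leaving. The upper-bound column shows that the opposite sign is possible.

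*A reader might infer a contradiction with the Treated Set.* The Treated Set says who is analysed; the completers rule says who has an observed value within it. The two can coexist. The table is incomplete as a description of the Treated Set, but not inconsistent with its definition.

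There is also real mitigation. Visit compliance and reasons for withdrawal will be presented (Protocol 10.2.3), and disposition counts those completing each visit and those leaving before Month 24 (SAP 12.2). A reader can therefore compute s/30. The SAP's binary worst-case rule would fit Class I versus not, although neither document makes that split. The Kaplan-Meier analysis uses withdrawn subjects' diaries up to event or censoring.

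These points rule out the stronger readings but leave the gap open. Compliance tables show how many are missing, not how they fared. Kaplan-Meier addresses a different outcome, time to first seizure with altered awareness, and itself assumes uninformative censoring. The bound that would settle the matter is optional.

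**Conclusion.** The point holds as a gap in a stated rule, with a possible but unproven upward bias. Both documents remove withdrawn treated subjects from later Engel and ILAE denominators, leave the Early Withdrawal class without a defined use there, and do not require any analysis showing how much this matters.

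Under the assumed values, the completers' share exceeds the all-failures bound by about 6 to 19 points and falls short of the all-successes bound by about 4 to 11 points. The first range is a worst case, not an estimate of the bias. In the six-withdrawal example, the shift is also smaller than the sampling uncertainty of about 20 points either side. It differs in kind, though: the confidence interval around the completers' share does not account for selective loss.

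Because the endpoint is secondary and descriptive, this is a change the sponsor should make and not a fault that undermines the study. The reason to act is that the figures are intended for pivotal-trial planning and the remedy is cheap.

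**What to change.** Amend SAP 11.1.3 and section 17, and align Protocol 10.1.3:

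1. At each visit, report every Engel and ILAE class over all Treated Set subjects due at that visit, with a missing/withdrawn row. Keep the completers' percentages alongside.
2. Show the Early Withdrawal class of withdrawn subjects in its own row or as a sensitivity analysis. Do not carry it forward as the main Month 24 result: a subject who was seizure-free on leaving at Month 4 would then count as Class I at Month 24, which could itself overstate success.
3. State in SAP section 17 that this is how available dropout data enter the surgical-outcome tables.
4. Change the permissive wording to a commitment for one analysis: a best-case/worst-case bound on Engel I versus not, and on ILAE 1 versus not, at 12 and 24 months. The split also supplies the binary form that the existing worst-case rule needs. Showing both bounds avoids counting seizure-free leavers against the device without qualification.

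The cost is SAP and protocol wording, some extra table rows, and a reported lower bound that is less favourable than the completers' figure. No new data collection is needed.

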10.1.4 Secondary Endpoint: Analysis of Quality of Life

Quality of life is assessed with the QOLIE-31 instrument. QOLIE-31 scores at baseline and each scheduled follow-up visit will be characterized using descriptive statistics. In addition, the per-subject paired change from baseline will be calculated and descriptive statistics reported for each scheduled follow-up visit. These analyses may be repeated for the QOLIE-31 sub-domains.

Longitudinal analysis of the QOLIE-31 scores may be performed using a generalized estimating equation (GEE) repeated measures model with a working AR1 correlation structure to estimate the mean (with 95% confidence intervals) of the QOLIE-31 over time while accounting for within subject correlation. Baseline QOLIE-31 and visit (categorical) will be included as covariates in the model. The estimate of QOLIE-31 score at 24 months is of primary interest.

Finally, the proportion of subjects with a change from baseline in QOLIE-31 score of 13 points or more will be calculated at each follow-up visit. The threshold of 13 points is based on previous literature estimating 13 points of QOLIE-31 to be the minimum clinically important difference.⁵ A 95% confidence interval for the proportion may be reported using the Clopper-Pearson exact method.

10.2 Statistical Analysis

10.2.1 General Principles

Standard summary statistics will be calculated for all study variables to be reported. For continuous variables, statistics will include means, standard deviations, medians and ranges. Categorical variables will be summarized by frequency distributions.

⁵ Wiebe S, Matijevic S, Eliasziw M, Derry PA. Clinically important change in quality of life in epilepsy. *J Neurol Neurosurg Psychiatr* 2002;73(2):116-120.

For any exploratory tests that are performed (e.g. change from baseline in endpoint measures), one-sided statistical tests will be deemed significant if the p-value is less than 0.025 while two-sided tests will be deemed significant if the p-value is less than 0.05. Statistical analyses will be conducted in SAS version 9.2 or above (SAS Institute, Cary, N.C.) or another validated statistical software package.

10.2.2 Analysis Populations

All subjects enrolled in the study (including those withdrawn from the investigation) will be accounted for and documented.

The following analysis populations are defined:

Enrolled Set: All subjects enrolled in the study

Treated Set: All subjects that initiate treatment with LITT (received thermal delivery with the NBS)

Per-protocol Set: All subjects in the Treated Set that are treated according to the protocol requirements and meet study and treatment eligibility criteria

In the feasibility study setting, conclusions about performance are best informed by analyses of the Treated Set. Analyses may be repeated on the Enrolled Set for full reporting of study results and on the Per-protocol Set to provide insight into the potential impact of protocol deviations on the analysis results.

10.2.3 Handling of Missing Data

The number and proportion of subjects eligible for and compliant with each follow-up examination will be presented. Subjects who withdraw from the study will be tabulated with reasons for withdrawal. Sensitivity analyses, such as multiple imputation or worst case imputation, may be performed to assess the robustness of study conclusions to the potential impact of missing data.

10.2.4 Sample Size

For this feasibility study, there are no hypothesis tests and therefore sample size is not based on power. Rather, the sample size of 30 subjects is based on providing a sufficiently robust characterization of adverse events and other study endpoints. With a sample size of 30 subjects, adverse events that have a 5% probability per-subject have approximately an 80% chance of being observed in at least one subject in the study. Study results obtained from a sample of 30 subjects will permit planning for the potential range of results that could occur in a larger pivotal trial.

10.3 Interim Analysis

Analyses will be performed on data from baseline through a major study time point once all subjects have completed that major study time point (e.g., 6 months, 12 months and 24 months). There is

minimal opportunity for bias since all procedures will have been completed before any analysis occurs and all data will have been collected for a time point before analysis of that time point is conducted.

10.4 Handling of Deviations from the Protocol Statistical Plan

Any departure or deviation from these planned statistical methodologies will be documented and discussed in the Statistical Analysis Plan and will include the statistical rationale for divergence.

11 RISK/BENEFIT ANALYSIS

A risk analysis according to International Organization for Standardization (ISO) 14971 (Application of Risk Management to Medical Devices) has been conducted as part of the CE Marking process. Risks have been minimized or eliminated through appropriate design control, and confirmed by pre-clinical bench, laboratory and animal testing.

11.1 Risks

As with any surgical procedure, the NBS involves some risks. The following potential risks or discomforts may be associated with the surgical procedure or the NBS. In addition, the list includes possible risks associated with the use of the NBS in an epilepsy population.

The frequency and severity of adverse events can vary, and may necessitate additional medical intervention, including surgery.

Agitation	Deep venous thrombosis	Obtundation
Anemia	Depression	Paralysis
Brain aneurysm	Difficulty hearing	Personality or cognitive changes (e.g. mood, memory, attention and thinking ability)
Anxiety	Difficulty speaking	Permanent neurological deficit
Aphasia	Difficulty swallowing	Pneumonia
Ataxia or loss of body coordination	Difficulty walking	Pain at incision site
Atelectasis	Hypotension	Pulmonary or other air embolism
Bacteremia or sepsis	Increased seizures	Reaction to anesthesia or other drugs
Bleeding into or around the brain	frequency/duration or severity, new seizure type, or status epilepticus	Stroke or transient ischemic attack (TIA)
Blurry vision/visual disturbance	Infection, local or generalized	Sudden unexpected death in epilepsy (SUDEP)
Cerebral infarction	Injury to blood vessels	Thromboembolism
Coma	Injury to brain tissue	Tingling or numb sensations in the body
Complete or incomplete hemiparesis	Insomnia	Tissue damage
Death	Intestinal toxicity	Unconsciousness
Decreased energy	Loss of mental function	Wound dehiscence
Drowsiness	Muscle weakness	
Edema	Myocardial infarction	
Failure of central regulation	Nausea/vomiting	
Fever	Nerve paralysis	
Headache		
Hypertension		

Additional possible risks from the evaluations required during this study (but not directly related to the use of the NBS) include:

Laboratory Testing Risks

For the pregnancy test, a blood sample will be taken by inserting a needle into a vein in the arm. Some risks of this procedure include fainting, infection, bruising, formation of a blood clot, pain, and/or bleeding at the site of the needle puncture.

Pregnancy Risks

The effects of LITT during pregnancy are unknown, and it is possible that harmful side effects could occur to both the mother and unborn child. For this reason, pregnant subjects are excluded from participation in this study. If the subject is a woman of childbearing age capable of becoming pregnant, they will be given a pregnancy test prior to entry into the study and again prior to the procedure.

Neuropsychological Testing Risks

The neuropsychological tests are either computer tests or paper and pencil tests. None of these tests pose any significant risk, although some persons may find the testing tedious or even frustrating. The testing, which can take up to 3 hours to perform, may be spread over two days. Breaks may be included during the testing to make it easier to complete.

MRI Risks

MRI uses large magnet fields. There are no known or foreseeable risks or side effects associated with MRI scanning procedures except for those people who have electrically, magnetically or mechanically activated implants, or metal in or on their bodies. A MRI scan is not uncomfortable but those prone to claustrophobia (fear of enclosed spaces) may become anxious.

Contrast Dye (Gadolinium) Risks

A contrast dye, gadolinium, may be used for the MRI. Possible side effects of a gadolinium injection include mild headache, nausea, and local pain, low blood pressure and lightheadedness. Very rarely, patients are allergic to gadolinium. These effects are most commonly hives and itchy eyes, but more severe reactions have been seen which result in shortness of breath.

